9.4.5.4 Electrocardiograms

Descriptive statistics will be produced at each schedule assessment timepoint for all quantitative ECG parameters (heart rate, PR, RR, QRS, QT, and QTcF intervals) for both observed absolute values and changes from baseline.

Electrocardiogram findings will also be listed.

An analysis of potentially clinically significant ECG values on QT, QTcF, QRS and PR interval, and heart rate will be performed. The number and percentage of patients with potentially clinically significant ECG values will be tabulated across time and treatment group. The criteria based on severity will be defined in the SAP.

Outliers with respect to QTcF will also be tabulated for the following categories:

- Absolute value > 450 ms
- Absolute value > 480 ms
- Absolute value > 500 ms

- Increase from baseline > 30 ms
- Increase from baseline > 60 ms

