5.2 Exclusion Criteria

Participants are excluded from the study if any of the following criteria apply:

Medical Conditions

- 1 Primary glomerulopathy, vasculitic renal disease (including ANCA-associated vasculitis), prior dialysis or unstable rapidly progressing renal disease, autosomal dominant or autosomal recessive polycystic kidney disease, lupus nephritis or ANCA-associated vasculitis.
- 2 Patients with currently decompensated HF requiring hospitalisation for optimisation of HF treatment and are not on stable HF therapy at the time of enrolment.
- 3 HF due to cardiomyopathies that would primarily require specific other treatment such as cardiomyopathy due to amyloidosis or infiltrative diseases, primary hypertrophic cardiomyopathy, cardiomyopathy related to current toxic or infective conditions (ie, ongoing chemotherapy, infective myocarditis, septic cardiomyopathy).
- 4 High output HF (eg, due to hyperthyroidism or Paget's disease).
- 5 HF due to pericardial disease, congenital heart disease or clinically significant uncorrected primary cardiac valvular disease or planned cardiac valve repair/replacement.
- 6 Patients with uncontrolled diabetes mellitus (HbA1c > 10%).
- 7 Patients with T1DM.
- 8 Intermittent or persistent 2nd or 3rd degree atrioventricular block, sinus node dysfunction with clinically significant bradycardia or sinus pauses, not treated with a pacemaker.
- 9 Known congenital long QT syndrome or history of QT prolongation associated with other medications.
- 10 History of any life-threatening cardiac dysrhythmia (continuous or paroxysmal) or uncontrolled ventricular rate in patients with atrial fibrillation or atrial flutter.
- 11 Acute coronary syndrome and/or elective/non-elective percutaneous cardiac interventions within 3 months prior to randomisation (Visit 3) or is planned to undergo any of these procedures during the study.
- 12 Any major cardiovascular (eg, open chest coronary artery bypass grafting or valvular repair/replacement) or major non-cardiovascular surgery as judged by the investigator within 3 months prior to randomisation (Visit 3) or is planned to undergo any of these procedures during the study.
- 13 Heart transplantation or left ventricular assist device at any time or if these are planned.
- 14 Kidney or any organ transplantation or if these are planned.
- 15 Addison's disease (a medical conditions associated with development of hyperkalaemia).

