- eGFR (mL/min/1.73 m^2) will be calculated using the BSA adjusted CKD-EPI formula and including both serum creatinine and serum cystatin C for central laboratory assessments, and with serum/plasma creatinine alone for local laboratory assessments. Extended formulas adopted for eGFR calculation are provided in Appendix B.
- The post-randomisation INR measurements may be done at a local laboratory if the necessary material provided by the central laboratory is not available; and the measurements may be omitted if the local laboratory is not capable of doing the measurements. Refer to Laboratory Manual for details.
- These tests are not required at screening or pre-randomization.
- g Per Friedewald equation
- h Central laboratory for all cystatin C measurements.

Laboratory parameters will be presented for each treatment group and/or visit.

The outlier laboratory values based on predefined criteria will be presented by treatment as defined in Table 3. A laboratory value will be considered abnormal if it meets the predefined criteria for the abnormality, except where the baseline value met the criteria for the abnormality and the new value is less extreme than the baseline value. Only the most severe value per participant will be accounted for.

Table 3 Laboratory abnormalities by predefined criteria

Blood Chemistry						
ALP Number of subjects with any on-treatment value >1.5x ULN >3x ULN	Total bilirubin  Number of subjects with any on-treatment value  >1.5x ULN  >2x ULN					
ALT Number of subjects with any on-treatment value >3x ULN >5x ULN >10x ULN >20x ULN	Na + (mmol/L)  Number of subjects with any on-treatment value  <120  <130  >150					

Blood Chemistry						
AST Number of subjects with any on-treatment value >3x ULN >5x ULN >10x ULN >20x ULN	K + (mmol/L)  Number of subjects with any on-treatment value ≤2.5					
ALT or AST  Number of subjects with any on-treatment value  >3x ULN  >5x ULN  >10x ULN  >20x ULN						
Haematocrit						
Haematocrit (Vol)  Number of subjects with any on-treatment value <0.20 >0.55 >0.60	Hemoglobin (g/L) Number of subjects with any on-treatment value <60 >180 >200					

For each scheduled post-baseline visit, descriptive statistics for all clinical chemistry and haematology parameters will be presented for observed values at each visit (including baseline) and change from baseline.

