# 4.11.5 Electrocardiogram

Single 12-lead ECG will be obtained after the patient has been resting in a supine position for at least 10 minutes, at the visits outlined in the SoA (Appendix A: Schedule of Activities).

A digital ECG machine that automatically calculates the heart rate and measures PR, QRS, QT, and QTc intervals will be used. Interpretation of the clinical safety digital ECG findings will be reviewed and confirmed by the investigator and recorded in the eCRF. Digital ECGs will be collected, cleaned, and stored by eResearch Technology (ERT).

Potentially clinically significant (PCS) ECG values will be identified based on the predefined criteria displayed in Table 6

Table 4 PCS ECG predefined criteria

Variable	Unit	Outside lower limit if	Outside upper limit if	AZ extended reference range - low	AZ extended reference range - high	Treatment emergent increase if	Extended treatment emergent increase if
Heart	bpm	<50	>100	<45	>120	NA	NA
rate				<30	>150		
RR	ms	<600	>1200	< 500	>1333	NA	NA
interval				<400	>2000		
PR interval	ms	<110	>220	<100	>240	>40	>60
QRS	ms	<75	>115	<70	>120	>15	>30
QT	ms	<320	>450	<300	>480	>30	>60
					>500		
QTcF	ms	<320	>450*	<300	>480*	>30*	>60*
					>500*	1	
QTcB	ms	<320	>450*	<300	>480*	>30*	>60*
					>500		

ms = milliseconds, bpm = beats per minute: NA= not applicable. Note, no standard criteria are established for treatment emergent increases or decreases in RR intervals or heart rates, or for treatment emergent decreases in PR, QRS or QT/QTc intervals.

Note, lower and upper RR interval limits and low and high RR interval reference ranges (all in ms), represent respectively the upper and lower heart rate limits and high and low heart rate reference ranges (all in bpm).

TP-GDO-WW-016-08 Effective Date: 26 Nov 19 Related to: SOP-GDO-WW-019

**Project Document Effective Date**: Date of last signature
Page 34 of 50

\*Cut-off values for categorical analyses as recommended by ICH E14 (Note, more than one category for high range increases in QT/QTc values).

The following summaries will be provided:

- A summary of the ECG variables and change from baseline in each ECG variable by treatment group and time point
- A summary of ECG assessment (normal/abnormal clinically significant/abnormal not clinically significant), baseline versus last observation on-treatment.
- A summary of the number and percentage of subjects reporting PCS ECG values outside predefined criteria, by ECG parameter, treatment and visit

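### The absolute-limit ECG counts have no baseline condition, so participants already beyond a limit before dosing stay in the counts and blur comparisons between arms

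*Protocol*

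**What the plan says.** Protocol 9.4.5.4 states: "The number and percentage of patients with potentially clinically significant ECG values will be tabulated across time and treatment group". For QTcF it lists absolute categories, starting with "Absolute value > 450 ms" and going on to 480 and 500 ms. It also lists change categories, "Increase from baseline > 30 ms" and then 60 ms.

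SAP 4.11.5 plans "A summary of the number and percentage of subjects reporting PCS ECG values outside predefined criteria, by ECG parameter, treatment and visit". Its Table 4 supplies two kinds of limit:

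- Absolute limits, among them QTcF > 450/480/500 ms, QRS > 115/120 ms, PR > 220/240 ms, and heart rate < 50 or > 100/120 bpm.
- Treatment-emergent increase limits for PR (> 40, > 60 ms), QRS (> 15, > 30 ms), and QT, QTcF and QTcB (> 30, > 60 ms). Heart rate and RR have none; the table note explains that "no standard criteria are established for treatment emergent increases or decreases in RR intervals or heart rates".

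The same section plans change from baseline for each ECG variable and "A summary of ECG assessment (normal/abnormal clinically significant/abnormal not clinically significant), baseline versus last observation on-treatment".

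For laboratory outliers, SAP 4.11.4 counts a value as abnormal when it meets the criterion, "except where the baseline value met the criteria for the abnormality and the new value is less extreme than the baseline value". No such sentence appears for ECGs. SAP 4.2 sets the default denominator as all participants in the analysis set and treatment group.

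**The concern.** A count beyond an absolute limit, with every participant in the denominator, mixes two groups: those who were beyond the limit before the first dose, and those who moved beyond it on treatment. Only the second group bears on the drug.

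This population can be expected to contain some of the first group. Inclusion criterion 5 provides for atrial fibrillation or flutter, exclusion criterion 8 leaves room for participants with a pacemaker, and section 6.5.2 covers participants with LVEF of 40% or less. The QT-related criterion is history-based ("Known congenital long QT syndrome or history of QT prolongation associated with other medications"), and the current text sets no numeric QTc ceiling.

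Protocol Table 2 names heart-rate, blood-pressure and ECG monitoring as the mitigation for the AZD9977 cardiovascular risk. If these counts consist mostly of standing abnormalities, the arms will look more alike on them than the new abnormalities would show.

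**Working it through.** **1. Which displays are affected.** ECGs are scheduled pre-dose at Visit 3 and then at Visits 4, 6, 8 and 10.

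| Display | Refers to baseline? |
|---|---|
| Absolute-limit counts by parameter, arm and visit | No |
| Increase limits for PR, QRS, QT, QTcF, QTcB | Yes |
| Mean change from baseline, all ECG variables | Yes |
| Overall ECG assessment, baseline versus last on-treatment | Yes, but not by parameter, and only at the last observation |
| Pulse-rate change of 20 bpm or more (SAP Table 5) | Yes |
| Laboratory outliers (SAP 4.11.4) | Yes |

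**2. What the increase rows miss.** Constructed examples of new crossings that stay below the increase limits:

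- QTcF 475 to 503 ms: crosses 480 and 500; the rise is 28, not > 30.
- QRS 110 to 122 ms: crosses 115 and 120; the rise is 12, not > 15.
- PR 210 to 245 ms: crosses 220 and 240; the rise is 35, not > 40.

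As categorical findings, these appear only in the absolute rows, pooled with participants who were already there.

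**3. Size of the dilution.** The plan states no figure to reproduce. The only input from the documents is 125 per arm; the rest are assumptions. Let p0 be the share beyond the limit at baseline, s the share of those still beyond it at a visit, and r the new-onset rate among the others.

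Observed proportion = p0 × s + (1 − p0) × r.

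Take s = 0.85 and r = 0.03 (control) or 0.06 (AZD9977 arm), a true ratio of 2.0. At p0 = 0.20:

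- Control: 0.20 × 0.85 + 0.80 × 0.03 = 0.194.
- AZD9977 arm: 0.20 × 0.85 + 0.80 × 0.06 = 0.218.
- Ratio: 0.218 / 0.194 = 1.12.

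Here z is the difference divided by its standard error, with n = 125 per arm for everyone, or 125 × (1 − p0) for those inside the limit at baseline.

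| p0 | Everyone: control vs active | Ratio | Difference | z | Inside at baseline: ratio | z |
|---|---|---|---|---|---|---|
| 10% | 11.2% vs 13.9% | 1.24 | 2.7 points | 0.64 | 2.0 | 1.09 |
| 20% | 19.4% vs 21.8% | 1.12 | 2.4 points | 0.47 | 2.0 | 1.03 |
| 30% | 27.6% vs 29.7% | 1.08 | 2.1 points | 0.37 | 2.0 | 0.96 |

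A larger assumed effect behaves the same way. With r = 0.03 against 0.12 (true ratio 4.0) and s = 1, counting everyone gives ratios of 2.09, 1.64, 1.32 and 1.13 at p0 = 5%, 10%, 20% and 40%.

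**4. Ratio versus difference.** The risk difference shrinks only by the factor (1 − p0), for example 3.0 × 0.80 = 2.4 points. The greater loss is in precision. At p0 = 0.20, chance imbalance in baseline outliers between two arms has standard deviation √(2 × 0.20 × 0.80 / 125) = 5.1 points. After 85% persistence that is 0.85 × 5.1 = 4.3 points, against a 2.4-point effect.

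**5. Would copying the laboratory rule be enough?** That rule drops a participant who was abnormal at baseline only when the new value is less extreme. If half of the baseline outliers read higher at a given visit (assumption), the proportion is p0 × 0.5 + (1 − p0) × r. The ratios become 0.104 / 0.077 = 1.35, 0.148 / 0.124 = 1.19 and 0.192 / 0.171 = 1.12 at 10%, 20% and 30%. The ratio of 2.0 returns only when the group is defined by baseline status alone.

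**The case against.** The strongest reply is that the ECG plan already looks at baseline in several ways, so this is a matter of presentation. Much of that stands. A reader might infer that ECG outliers have no baseline reference at all. Table 4 contradicts this for PR, QRS, QT, QTcF and QTcB, and mean changes are planned throughout. A reader might also infer that heart rate, the parameter raised by the dog toxicology, has no baseline-referenced count. The ECG table has none, but SAP Table 5 defines pulse-rate changes of 20 bpm or more and counts them by arm, and pulse is taken at more visits than the ECG.

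Other mitigations also stand. Exclusion 9 removes known congenital long QT and QT prolongation associated with other medications. Exclusion 10 removes uncontrolled ventricular rate in atrial fibrillation or flutter. Participants who entered before Amendment 4 faced a QTcF ceiling of 470 ms, though that still admits values above 450. Clinically relevant new or worsening ECG findings must be recorded as adverse events (protocol 8.2.3). Randomisation balances baseline outliers in expectation, and no ECG test is planned.

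The by-visit table may also include Visit 3, since its layout is left to the TFL shells. That would help but not suffice: 20% at baseline and 20% at Visit 8 fits both no movement and equal numbers moving in and out.

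None of this supplies a count of new crossings by parameter.

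**Conclusion.** The point holds for the absolute-limit counts and for conclusions drawn from them. Participants beyond a limit before dosing are carried into those counts, and the increase rows do not capture smaller new crossings. The direction follows from the text. The size does not: the baseline rate, persistence and onset rates in the illustration are assumptions.

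Two stronger readings are not supported. One is that any drug effect on the ECG is diluted or hidden; mean changes, increase rows and pulse-rate changes are untouched. The other is that the counts would lead to a wrong formal conclusion; the tables are descriptive, and with 3% against 6% the illustrative z stays near 1 even in the cleaner comparison. What is lost is clarity in a cardiac safety display, and it can be restored from data already collected.

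**What to change.** In SAP 4.11.5, for each absolute limit in Table 4:

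1. Add the number and percentage of participants inside the limit at baseline who go outside it on treatment. The denominator is participants inside that limit at baseline who have a post-baseline ECG.
2. Report worsening among those already outside at baseline separately, or give a per-parameter shift table of baseline against worst on-treatment category. Do not add worsened cases to the denominator in item 1, because it would then depend on the outcome.
3. Keep the all-participant counts and show the baseline count beside them.

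No new data are needed. The cost is SAP wording, a baseline flag and one more row or table, with a somewhat smaller denominator in the new-onset rows (for example 125 × 0.80 = 100 per arm if 20% start outside).

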9.4.5.5 Physical Examination

The listings of the physical examination will include date of examination and confirmation of assessment performed (Yes/No).

9.4.5.6 Safety Topics of Interest

Hyperkalaemia

Hyperkalaemia will be evaluated by the analysis of serum/plasma K⁺ levels (eg, absolute values and change from baseline, values outside predefined ranges, values meeting protocol-defined discontinuation criteria for hyperkalaemia). Further details will be provided in the SAP.

Hypotension

Symptomatic hypotension/decreased blood pressure will be evaluated by the analysis of BP measurements (eg, values outside predefined ranges) and the analysis of pre-defined AE PTs related to hypotension, as well as discontinuations due to hypotension. Further details will be provided in the SAP.

Deteriorating Renal Function

Deteriorating renal function will be evaluated by analysis of serum creatinine and eGFR values (eg, percent change from baseline in eGFR, absolute values and change from baseline, values meeting protocol-defined discontinuation criteria for deteriorating renal function) and analysis of pre-defined AE PTs related to deteriorating renal function. Further details will be provided in the SAP.

9.5 Interim Analyses

An interim analysis will be performed when 300 patients have been treated for 12 weeks, unless the planned date of the interim analysis is too close to the expected data base lock date, for the complete study. The purpose of the interim analysis is to have the possibility to trigger Phase 3 activities; therefore, there will be no alpha spent. The conduct of the study will not be impacted by the results of the interim analysis. The decision to conduct an interim analysis will be documented.

The SAP will describe the planned interim analyses in greater details.

9.6 Data Monitoring Committee

A Safety Unblinded Data Review Committee will be set up for this study for ongoing safety monitoring. In addition to general safety/tolerability, the committee will focus on potential

risks related to hypotension, deteriorating renal function and hyperkalaemia. An Interim Unblinded Data Review Committee will be set up to review data from the pre-planned interim analysis and make recommendations on future clinical development.

For details on the review committee, refer to Appendix A 5.

10 SUPPORTING DOCUMENTATION AND OPERATIONAL CONSIDERATIONS

Appendix A Regulatory, Ethical, and Study Oversight Considerations

A 1 Regulatory and Ethical Considerations

- This study will be conducted in accordance with the protocol and with the following:
 - Consensus ethical principles derived from international guidelines including the Declaration of Helsinki and CIOMS International Ethical Guidelines
 - Applicable ICH GCP Guidelines
 - Applicable laws and regulations
- The protocol, protocol amendments, ICF, Investigator Brochure, and other relevant documents (eg, advertisements) must be submitted to an IRB/IEC by the investigator and reviewed and approved by the IRB/IEC before the study is initiated.
- Any amendments to the protocol will require IRB/IEC and applicable Regulatory Authority approval before implementation of changes made to the study design, except for changes necessary to eliminate an immediate hazard to study participants.
- AstraZeneca will be responsible for obtaining the required authorisations to conduct the study from the concerned Regulatory Authority. This responsibility may be delegated to a CRO, but the accountability remains with AstraZeneca.

Regulatory Reporting Requirements for SAEs

- Prompt notification by the investigator to the sponsor of a SAE is essential so that legal obligations and ethical responsibilities towards the safety of participants and the safety of a study intervention under clinical investigation are met.
- The sponsor has a legal responsibility to notify both the local regulatory authority and other regulatory agencies about the safety of a study intervention under clinical investigation. The sponsor will comply with country-specific regulatory requirements relating to safety reporting to the regulatory authority, IRB/IEC, and investigators.
- For all studies except those utilising medical devices investigator safety reports must be prepared for SUSARs according to local regulatory requirements and sponsor policy and forwarded to investigators as necessary.
- An investigator who receives an investigator safety report describing a SAE or other specific safety information (eg, summary or listing of SAEs) from the sponsor will review and then file it along with the [Investigator's Brochure or state other documents] and will notify the IRB/IEC, if appropriate according to local requirements.

A 2 Financial Disclosure

Investigators and sub-investigators will provide the sponsor with sufficient, accurate financial information as requested to allow the sponsor to submit complete and accurate financial

certification or disclosure statements to the appropriate regulatory authorities. Investigators are responsible for providing information on financial interests during the course of the study and for 1 year after completion of the study.

A 3 Informed Consent Process

- The investigator or his/her representative will explain the nature of the study to the participant or his/her legally authorised representative and answer all questions regarding the study.
- A pre-screening ICF and/or a full ICF have to be signed before any study intervention will take place.
- Participants must be informed that their participation is voluntary, and they are free to refuse to participate and may withdraw their consent at any time and for any reason during the study. Participants will be required to sign a statement of informed consent that meets the requirements of 21 CFR 50, local regulations, ICH guidelines, HIPAA requirements, where applicable, and the IRB/IEC or study centre.
- The medical record must include a statement that written informed consent was obtained before the participant was enrolled in the study and the date the written consent was obtained. The authorised person obtaining the informed consent must also sign the ICF.
- Participants must be re-consented to the most current version of the ICF(s) during their participation in the study.
- A copy of the ICF(s) must be provided to the participant or the participant's legally authorised representative.

Participants who are rescreened are required to sign a new ICF.

The ICF will contain a separate section that addresses and documents the collection and use of any mandatory and/or optional human biological samples. The investigator or authorised designee will explain to each participant the objectives of the analysis to be done on the samples and any potential future use. Participants will be told that they are free to refuse to participate in any optional samples or the future use and may withdraw their consent at any time and for any reason during the retention period.

A 4 Data Protection

- Participants will be assigned a unique identifier by the sponsor. Any participant records or datasets that are transferred to the sponsor and its research collaborators will contain the identifier only; participant names or any information which would make the participant identifiable will not be transferred.
- The participant must be informed that his/her personal study-related data will be used by the sponsor and its research collaborators in accordance with local data protection law.

The level of disclosure and use of their data must also be explained to the participant in the informed consent.

• The participant must be informed that his/her medical records may be examined by Clinical Quality Assurance auditors or other authorised personnel appointed by the sponsor, by appropriate IRB/IEC members, and by inspectors from regulatory authorities.

A 5 Committees Structure

A Safety Unblinded Data Review Committee will be set up for this study to monitor general safety/tolerability, with a focus on hypotension, deteriorating renal function and hyperkalaemia.

An Interim Unblinded Data Review Committee will be set up to review data from the pre-planned interim analysis and make recommendations regarding future clinical development.

The safety of all AstraZeneca clinical studies is closely monitored on an ongoing basis by AstraZeneca representatives in consultation with Patient Safety. Issues identified will be addressed; for instance, this could involve amendments to the CSP and letters to investigators.

A 6 Dissemination of Clinical Study Data

A description of this clinical study will be available on http://astrazenecaclinicaltrials.com and http://www.clinicaltrials.gov as will the summary of the main study results when they are available. The clinical study and/or summary of main study results may also be available on other websites according to the regulations of the countries in which the main study is conducted.

A 7 Data Quality Assurance

- All participant data relating to the study will be recorded on eCRF unless transmitted to the sponsor or designee, and its research collaborators, electronically (eg, laboratory data). The investigator is responsible for verifying that data entries are accurate and correct by physically or electronically signing the eCRF.
- The investigator must maintain accurate documentation (source data) that supports the information entered in the eCRF.
- The investigator must permit study-related monitoring, audits, IRB/IEC review, and regulatory agency inspections and provide direct access to source data documents.
- Monitoring details describing strategy (eg, risk-based initiatives in operations and quality such as Risk Management and Mitigation Strategies and Analytical Risk-Based Monitoring), methods, responsibilities and requirements, including handling of

non-compliance issues and monitoring techniques (central, remote, or on-site monitoring) are provided in the Monitoring Plan.

- The sponsor or designee, and its research collaborators are responsible for the data management of this study including quality checking of the data.
- The sponsor assumes accountability for actions delegated to other individuals (eg, CROs).
- Study monitors will perform ongoing source data verification to confirm that data entered into the eCRF by authorised site personnel are accurate, complete, and verifiable from source documents; that the safety and rights of participants are being protected; and that the study is being conducted in accordance with the currently approved protocol and any other study agreements, ICH GCP, and all applicable regulatory requirements.
- Records and documents, including signed ICFs, pertaining to the conduct of this study must be retained by the investigator for 15 years after study completion unless local regulations or institutional policies require a longer retention period. No records may be destroyed during the retention period without the written approval of the sponsor. No records may be transferred to another location or party without written notification to the sponsor.

A 8 Source Documents

- Source documents provide evidence for the existence of the participant and substantiate the integrity of the data collected. Source documents are filed at the investigator's site.
- Data reported on the eCRF or entered in the eCRF that are transcribed from source documents must be consistent with the source documents or the discrepancies must be explained. The investigator may need to request previous medical records or transfer records, depending on the study. Also, current medical records must be available.
- Definition of what constitutes source data can be found in the source data agreement and computerised data checklist for electronic source data.

A 9 Study and Site Start and Closure

The study start date is the date on which the clinical study will be open for recruitment of participants.

The first act of recruitment is the first patient enrolled (ie, who signed consent) and will be the study start date.

The sponsor designee reserves the right to close the study site or terminate the study at any time for any reason at the sole discretion of the sponsor. Study sites will be closed upon study completion. A study site is considered closed when all required documents and study supplies have been collected and a study site closure visit has been performed.

The investigator may initiate study site closure at any time, provided there is reasonable cause and sufficient notice is given in advance of the intended termination.

Reasons for the early closure of a study site by the sponsor or investigator may include but are not limited to:

- Failure of the investigator to comply with the protocol, the requirements of the IRB/IEC or local health authorities, the sponsor's procedures, or GCP guidelines
- Inadequate recruitment of participants by the investigator
- Discontinuation of further study intervention development

If the study is prematurely terminated or suspended, the sponsor shall promptly inform the investigators, the IECs/IRBs, the regulatory authorities, and any CRO(s) used in the study of the reason for termination or suspension, as specified by the applicable regulatory requirements. The investigator shall promptly inform the participant and should assure appropriate participant therapy and/or follow-up.

Participants from terminated sites will have the opportunity to be transferred to another site to continue the study.

A 10 Publication Policy

- The results of this study may be published or presented at scientific meetings. If this is foreseen, the investigator agrees to submit all manuscripts or abstracts to the sponsor before submission. This allows the sponsor to protect proprietary information and to provide comments.
- The sponsor will comply with the requirements for publication of study results. In accordance with standard editorial and ethical practice, the sponsor will generally support publication of multi-centre studies only in their entirety and not as individual site data. In this case, a co-ordinating investigator will be designated by mutual agreement.
- Authorship will be determined by mutual agreement and in line with International Committee of Medical Journal Editors authorship requirements.

Appendix B Adverse Events: Definitions and Procedures for Recording, Evaluating, Follow-up, and Reporting

B1 Definition of Adverse Events

An AE is the development of any untoward medical occurrence in a participant or clinical study participant administered a medicinal product and which does not necessarily have a causal relationship with this treatment. An AE can therefore be any unfavourable and unintended sign (eg, an abnormal laboratory finding), symptom (for example nausea, chest pain), or disease temporally associated with the use of a medicinal product, whether or not considered related to the medicinal product.

The term AE is used to include both serious and non-serious AEs and can include a deterioration of a pre-existing medical occurrence. An AE may occur at any time, including run-in or washout periods, even if no study treatment has been administered.

B 2 Definitions of Serious Adverse Event

A SAE is an AE occurring during any study period (ie, run-in, treatment, washout, follow-up), that fulfils one or more of the following criteria:

- Results in death
- Is immediately life-threatening
- Requires in-participant hospitalisation or prolongation of existing hospitalisation
- Results in persistent or significant disability or incapacity
- Is a congenital anomaly or birth defect
- Is an important medical event that may jeopardise the participant or may require medical treatment to prevent one of the outcomes listed above

Adverse events for **malignant tumours** reported during a study should generally be assessed as **serious** AEs. If no other seriousness criteria apply, the 'Important Medical Event' criterion should be used. In certain situations, however, medical judgement on an individual event basis should be applied to clarify that the malignant tumour event should be assessed and reported as a **non-serious** AE. For example, if the tumour is included as medical history and progression occurs during the study, but the progression does not change treatment and/or prognosis of the malignant tumour, the AE may not fulfil the attributes for being assessed as serious, although reporting of the progression of the malignant tumour as an AE is valid and should occur. Also, some types of malignant tumours, which do not spread remotely after a routine treatment that does not require hospitalisation, may be assessed as non-serious; examples in adults include Stage 1 basal cell carcinoma and Stage 1A1 cervical cancer removed via cone biopsy.

Life-threatening

'Life-threatening' means that the participant was at immediate risk of death from the AE as it occurred, or it is suspected that use or continued use of the product would result in the participant's death. 'Life-threatening' does not mean that had an AE occurred in a more severe form it might have caused death (eg, hepatitis that resolved without hepatic failure).

Hospitalisation

Outpatient treatment in an emergency room is not in itself a serious AE, although the reasons for it may be (eg, bronchospasm, laryngeal oedema). Hospital admissions and/or surgical operations planned before or during a study are not considered AEs if the illness or disease existed before the participant was enrolled in the study, provided that it did not deteriorate in an unexpected way during the study.

Important Medical Event or Medical Treatment

Medical and scientific judgement should be exercised in deciding whether a case is serious in situations where important medical events may not be immediately life-threatening or result in death, hospitalisation, disability or incapacity but may jeopardise the participant or may require medical treatment to prevent one or more outcomes listed in the definition of serious. These should usually be considered as serious.

Simply stopping the suspect drug does not mean that it is an important medical event; medical judgement must be used. Below are some examples of events that may be considered medically important based on the investigator's judgement:

- Angioedema not severe enough to require intubation but requiring iv hydrocortisone treatment
- Hepatotoxicity caused by paracetamol (acetaminophen) overdose requiring treatment with N-acetylcysteine
- Intensive treatment in an emergency room or at home for allergic bronchospasm
- Blood dyscrasias (eg, neutropenia or anaemia requiring blood transfusion, etc.) or convulsions that do not result in hospitalisation
- Development of drug dependency or drug abuse

Intensity Rating Scale

- mild (awareness of sign or symptom, but easily tolerated)
- moderate (discomfort sufficient to cause interference with normal activities)
- severe (incapacitating, with inability to perform normal activities)

It is important to distinguish between serious and severe AEs. Severity is a measure of

intensity whereas seriousness is defined by the criteria in Appendix B 2. An AE of severe intensity need not necessarily be considered serious. For example, nausea that persists for several hours may be considered severe nausea, but not a SAE unless it meets the criteria shown in Appendix B 2. On the other hand, a stroke that results in only a limited degree of disability may be considered a mild stroke but would be a SAE when it satisfies the criteria shown in Appendix B 2.

B3 A Guide to Interpreting the Causality Question

When making an assessment of causality consider the following factors when deciding if there is a 'reasonable possibility' that an AE may have been caused by the drug.

- Time Course. Exposure to suspect drug. Has the participant actually received the suspect drug? Did the AE occur in a reasonable temporal relationship to the administration of the suspect drug?
- Consistency with known drug profile. Was the AE consistent with the previous knowledge of the suspect drug (pharmacology and toxicology) or drugs of the same pharmacological class? Or could the AE be anticipated from its pharmacological properties?
- De-challenge experience. Did the AE resolve or improve on stopping or reducing the dose of the suspect drug?
- No alternative cause. The AE cannot be reasonably explained by another aetiology such as the underlying disease, other drugs, other host, or environmental factors.
- Rechallenge experience. Did the AE reoccur if the suspected drug was reintroduced after having been stopped? AstraZeneca would not normally recommend or support a rechallenge.
- Laboratory tests. A specific laboratory investigation (if performed) has confirmed the relationship.

In difficult cases, other factors could be considered such as:

- Is this a recognised feature of overdose of the drug?
- Is there a known mechanism?

Causality of 'related' is made if following a review of the relevant data, there is evidence for a 'reasonable possibility' of a causal relationship for the individual case. The expression 'reasonable possibility' of a causal relationship is meant to convey, in general, that there are facts (evidence) or arguments to suggest a causal relationship.

The causality assessment is performed based on the available data including enough

information to make an informed judgement. With no available facts or arguments to suggest a causal relationship, the event(s) will be assessed as 'not related'.

